### 2.3.4 Eligibility Assessment

All primary care visits that take place at all randomized clinics after the CI-CDS system is implemented will be screened for intervention eligibility. Each time the vitals tab of the EPIC electronic health record (EHR) interface is closed (e.g., during the rooming process of nearly all primary care visits) the web service is programmed to automatically run a series of algorithms. The data elements needed to execute these algorithms, including eligibility algorithms, are gathered from EPIC and sent to the web service. The eligibility algorithms confirm that the person is age-eligible, search for prior cognitive screening and assessment data, run the algorithm to estimate risk of CI, and confirm that the patient does not already have a diagnosis of CI and that none of the exclusion criteria apply. They automatically and passively assess each web service call for CI-CDS eligibility without awareness or involvement of a front-end user. The platform additionally documents all eligibility assessments (i.e., eligible and ineligible) so that the characteristics of visits and patients screened for eligibility can be quantified as each

eligibility criterion is applied. This process results in eligibility being assessed and documented consistently for all patients at all randomized study clinics. Patients will be accrued into the study on the date of their first visit during the accrual period that meets all intervention eligibility criteria (i.e., index visit), and followed for the duration of the observation period.

When a patient is deemed eligible for CI-CDS content, a second set of algorithms use up to 5 years of clinical information stored in the EHR to assemble the intervention content (treatment recommendations) that should be presented to the clinician. Display rules determine whether the visit is occurring in a clinic randomized to present the intervention content to the clinician (i.e., CI-CDS) or not (i.e., UC). Trace data documenting the results of each of these sets of algorithms are stored in the web service. The study team retrospectively extracts the trace data from the web service to know how many index visits or intervention-eligible visits have occurred and with how many patients, and to know the content assembled for each of these visits.

## 2.4 Study Measures and outcome definitions

### 2.4.1 H1 outcome (primary): CI detection

The primary study outcome is CI detection. CI detection will be a binary outcome calculated from EHR data that is present if an ICD-10 diagnostic code for CI (dementia or mild cognitive impairment [MCI]) is documented at an outpatient or inpatient encounter, or added to the problem list, between the index visit and the end of the observation period, inclusive. The diagnostic codes that will denote CI detection will be the same as those used in determining eligibility (section 2.3.3). The data elements needed to calculate this outcome will be extracted at the conclusion of the observation period from the EHR of patients in the ITT population. It is hypothesized that patients in CI-CDS clinics will be more likely to have CI detected than patients in UC clinics.

### 2.4.2 H2 outcome (secondary): Clinician confidence

#### 2.4.2.1 Clinician confidence definitions

Clinician confidence in diagnosing CI will be measured by a single survey item (How confident are you in your ability to diagnose cognitive impairment, including mild cognitive impairment or dementia?), followed by 5 items asking about confidence with specific components or steps of diagnosis (e.g., confidence conducting a cognitive assessment using tools like the MoCA, or distinguishing between types of dementia).

Confidence in managing CI care will be measured similarly. An overall confidence item (How confident are you in your ability to manage care for patients with cognitive impairment?) will be followed by 9 items addressing confidence in conducting specific care management activities (e.g., providing pharmacological treatment, accessing patient education materials).

The response options for all clinician confidence items will be a 4-point rating scale (not at all, a little, moderately, or very confident). Responses may be dichotomized prior to analysis (e.g., moderately or very vs. little or not at all).

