9.4.2 Secondary outcomes

A secondary outcome will be clinician-reported confidence in management of CI care (H2). The pre-and post-implementation clinician surveys in both study arms will include a series of Likert-scale survey items based on previous literature to assess confidence to correctly assess and diagnose CI.[14, 27] Items will ask about confidence in diagnosis and management of CI care generally and will include items about specific elements such as conducting appropriate testing and patient and care partner education. Items will be analyzed individually, and composite measures of confidence will be considered.

Another secondary outcome will be health care utilization among accrued patients with HealthPartners insurance (H3). Indicators of any use of emergency room (ER), inpatient or both facility types between the index visit and of the observation period, inclusive, will be calculated from data extracted from insurance claims databases. Additionally, the combined costs of ER and inpatient care delivered will be extracted as paid amounts for facility and professional services on ER and inpatient days.

Patient and clinician characteristics that could moderate the effectiveness of the CI-CDS system on these primary and secondary outcomes will also be extracted from the EHR and clinician surveys. EHR-based data include patient encounters (number and type), demographics (e.g., age, gender, race, ethnicity), social determinants of health (e.g., insurer, area deprivation index score for home address, median education for Census tract of home address, country of origin, need for interpreter) and comorbidities present at index (e.g., diabetes, cardiovascular disease, mental illnesses, substance use). Potential clinician moderators include clinician self-reported years in practice, sex, provider type and specialty.

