9.5.3. Secondary outcomes

H2 predicts that clinicians practicing in CI-CDS relative to UC clinics will report more post-implementation confidence in diagnosing and managing CI. We will also use a LMM approach for the H2 analyses. The distributional properties of the confidence and management composites calculated from post-implementation clinician survey data will inform how to specify the distribution and link functions for these variables (e.g., normal-identity, Poisson-log, binomial-logit, binomial-log, multinomial-cumulative logit). The fixed CI-CDS parameter and random clinic intercept from the H1 model will be retained, and a fixed parameter for the outcome value reported in the pre-implementation clinician survey will be added. Exploratory analyses will assess whether the relationship between CI-CDS and either of these outcomes is more pronounced among clinician subgroups (e.g., clinician type).

H3 predicts that patients accrued from CI-CDS clinics will have lower post-index health care utilization. Anticipating a zero-mass of patients with no emergency department or inpatient costs, we will employ a 2-part model to test H3.[86] In the first part, the probability that patients will experience one or more emergency department visits or inpatient stays will be assessed using logistic regression in the same form as was used for H1. The second part will employ a generalized linear model (GLM)[87, 88] allowing clustering by clinic and controlling for demographics and baseline risk. Such analyses often specify a gamma distribution for health care expenditures with a log link function of the explanatory variables. We will choose the distribution family based upon the data using a modified Park test and choose the link function using a Box-Cox test.[89] If we observe a statistically significant reduction in emergency department and inpatient costs in the CI-CDS group, we will use similar methods to assess whether total costs of care, including all outpatient care and pharmacy, are also lower.

Analyses of secondary and exploratory patient outcomes will also follow the same analytic approach as the H1 model with appropriate modifications to the link function and error distribution.

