### 3.3 Secondary analyses

#### 3.3.1 Clinician confidence (H2).

The H2 analyses, comparing clinician confidence following CI-CDS implementation to pre-implementation by treatment arm, will be carried out using all available data from PCCs who responded to either survey. Descriptive statistics will be used to characterize PCC respondents, assess the distributional properties of items from which the H2 outcomes (i.e., confidence in diagnosing and in managing CI) will be calculated and estimate clinic and PCC intraclass correlations. The distributional properties of the confidence ratings will inform how to specify the distribution and link functions for these variables (e.g., normal-identity, binomial-logit). Because ratings are unlikely to approximate a normal distribution, the anticipated H2 models are generalized LMMs to account for repeated ratings from PCCs and a link to normalize the binary outcomes:

$$\text{logit}(\text{confidence}_{it}) = \gamma_{00} + \gamma_{10}\text{CI-CDS}_i + \gamma_{01}\text{post-CI-CDS}_{it} + \gamma_{11}\text{CI-CDS}_i * \text{post-CI-CDS}_{it} + [\nu_i], \quad \text{where } i=\text{PCC}, t=\text{survey time}.$$

Parameter  $\gamma_{11}$  is expected to be positive and statistically significant, indicating more increase in confidence from pre- to post-CI-CDS implementation among PCCs at CI-CDS clinics relative to PCCs at UC clinics. Model-estimated outcomes will be calculated by treatment group and time. Change in confidence will be presented within each treatment group as an OR or RR and 95% CI. The relative OR (i.e., ROR =  $\text{OR}_{\text{CI-CDS}} / \text{OR}_{\text{UC}}$ ) and its 95% confidence interval will estimate the difference across treatment arms in change in confidence.

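### H2: whether, and where, the 4-point confidence ratings are cut in two is left open, and the only model written is a binary logit that uses less of the scale than an ordinal model would

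*SAP*

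**What the plan says.** SAP 2.4.2.1 defines one overall diagnosing item with 5 component items, and one overall managing item with 9 component items. On the scale it states: "The response options for all clinician confidence items will be a 4-point rating scale (not at all, a little, moderately, or very confident"). It adds: "Responses may be dichotomized prior to analysis (e.g., moderately or very vs. little or not at all"). The cut is conditional and appears only as an example.

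SAP 3.3.1 says: "The distributional properties of the confidence ratings will inform how to specify the distribution and link functions for these variables (e.g., normal-identity, binomial-logit"). It expects the ratings not to be close to normal and on that ground states that "the anticipated H2 models are generalized LMMs to account for repeated ratings from PCCs and a link to normalize the binary outcomes". The one H2 equation is a logit model with arm, survey time and their interaction. Results are to be reported as odds ratios or risk ratios, and as a relative odds ratio between arms.

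Protocol 9.5.3 gives a longer list of example distribution-link pairs for the confidence and management composites: "normal-identity, Poisson-log, binomial-logit, binomial-log, multinomial-cumulative logit". The model there is different: a post-survey outcome adjusted for the pre-survey value. Protocol 9.4.2 says: "Items will be analyzed individually, and composite measures of confidence will be considered".

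Neither document gives a reason for dichotomising, a rule for when it will happen, or a sample size or power calculation for H2.

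**The concern.** Two things are at stake.

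**Discretion.** A four-level item can be cut in three places. With 6 diagnosing and 10 managing items, possible composites, and a link to be informed by the observed ratings, the H2 test can take many forms. Study personnel are not blinded to clinic assignment (SAP 2.2). A test expected to give a statistically significant interaction should not depend on choices made once the ratings are visible.

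**Information.** With the example cut, a clinician who moves from *not at all* to *a little*, or from *moderately* to *very*, counts as unchanged. Non-normality is the only reason given for leaving a normal model, and it does not call for a binary outcome. A cumulative-logit model handles ordered, non-normal ratings directly, uses all four levels, needs no cut, and keeps the arm-by-time relative odds ratio.

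**Working it through.** The documents give no H2 sample size or effect size, so there is no plan figure to reproduce. The check is how much information the example cut keeps.

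**Inputs**
- Four levels per item; example cut *moderately/very* against *a little/not at all* (SAP 2.4.2.1).
- Pilot share in the two lowest levels: 57% for diagnosing overall and 71% for managing overall, N=14 (Protocol 15.3).
- The split within each half is not given. Two sets of assumptions are used: (i) the extreme level holds 10% to 50% of its half, varied separately in each half; (ii) three specific splits of the 57/43 marginal, (0.05, 0.52, 0.38, 0.05), (0.12, 0.45, 0.35, 0.08) and (0.15, 0.42, 0.30, 0.13), with the same within-half proportions carried over to 71/29.

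**Formula.** In a two-group comparison under proportional odds, information on the log odds ratio is proportional to 1 - Σp³ over the levels. After a cut with a share p in the low half, this becomes 1 - p³ - (1-p)³ = 3p(1-p).

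**Two-level values**
- Diagnosing: 3 × 0.57 × 0.43 = 0.735
- Managing: 3 × 0.71 × 0.29 = 0.618

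**Four-level values and ratios**

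| Item and assumed split | Level shares | 1 - Σp³ | Kept by the cut | More clinicians needed |
|---|---|---|---|---|
| Diagnosing, extremes 10% of each half | 0.057, 0.513, 0.387, 0.043 | 0.807 | 0.911 | 10% |
| Diagnosing, extremes 50% of each half | 0.285, 0.285, 0.215, 0.215 | 0.934 | 0.787 | 27% |
| Diagnosing, sparsest specific split | 0.05, 0.52, 0.38, 0.05 | 0.804 | 0.914 | 9% |
| Managing, extremes 10% of each half | 0.071, 0.639, 0.261, 0.029 | 0.721 | 0.857 | 17% |
| Managing, extremes 50% of each half | 0.355, 0.355, 0.145, 0.145 | 0.904 | 0.683 | 46% |
| Managing, sparsest specific split carried over | 0.062, 0.648, 0.256, 0.034 | 0.711 | 0.869 | 15% |

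First row in full: 1 - (0.0002 + 0.1350 + 0.0580 + 0.0001) = 0.807; 0.735/0.807 = 0.911; 0.807/0.735 - 1 = 10%.

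Taken together, the cut keeps about 68-91%. The extra clinicians needed are 9-27% for diagnosing and 15-46% for managing.

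**What this could mean for power (illustration only).** The pilot had 25 eligible clinicians in 3 clinics. Scaled to 30-38 clinics, that is 250-317 clinicians. At the 60% response expected in Protocol 6.2.5, about 150-190 respond, or 75-95 per arm. Assume a common odds ratio of 2.0 and two-sided 0.05. Power is Φ(√V × ln 2 - 1.96), where V = (n per arm/6) × (1 - Σp̄³) and p̄ averages the two arms.

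For diagnosing after the cut with 75 per arm, the odds of a high rating rise from 0.43/0.57 = 0.754 to 1.509, so the low share falls from 0.57 to 0.399, with a mean of 0.484. Then V = 12.5 × 3 × 0.484 × 0.516 = 9.37, and power is Φ(3.06 × 0.693 - 1.96) = 56%.

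| Item | n per arm | Two levels | Four levels |
|---|---|---|---|
| Diagnosing | 75 | 56% | 60-66% |
| Diagnosing | 95 | 67% | 71-76% |
| Managing | 75 | 54% | 58-65% |
| Managing | 95 | 64% | 68-76% |

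The gain is about 4 to 12 percentage points. These figures ignore clinic clustering and repeated ratings, so only the comparison between columns is useful.

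**The case against.** A reader might infer that the SAP commits to dichotomising. It does not: the cut is optional, the binary model is anticipated rather than fixed, and the example list includes a normal-identity model that would use all four levels. The binary model is also named in advance; only a departure from it would follow the data.

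A reader might also infer that the SAP abandons an ordinal analysis the protocol required. That is not supported either. The cumulative logit is one of five examples, attached to composites in a differently built model, and the same list contains binomial-logit. The SAP's shorter list is also only illustrative.

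The example cut is not arbitrary, since the pilot tables in Protocol 15.3 group every confidence item that way. That makes it a sensible choice, but the SAP does not lock it.

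The size of the loss is uncertain. The marginals come from 14 pre-intervention clinicians, and the pilot items asked about diagnosing or managing without specialist referral, which the SAP items do not. The formula is for an independent two-group comparison, whereas H2 tests an arm-by-time interaction with a clinician random intercept. It does not apply to composites. A single figure for managing, such as the 41% that follows from (0.25, 0.46, 0.25, 0.04), would present one assumed split as a result. Nor does a 60% response rate by itself show that precision is poor, since that depends on the number of clinicians, which neither document gives for H2.

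The ordinal model has a cost too. If an extreme level holds 4-5% of responses, that is about 3-4 clinicians per arm at 75 per arm, and proportional odds is then hard to check.

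What stands: whether and where to cut is open, the only written model discards ordering within each half, and the stated reason does not require it.

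**Conclusion.** The point holds as a low-cost improvement to a secondary outcome. The SAP leaves dichotomisation, its cut point and the final link open, and anticipates a binary logit where an ordinal model would suit the scale better. The discretion part rests on the text alone. The efficiency part rests on proportional odds, assumed within-half splits and small pilot marginals, so the ranges above indicate a likely direction and rough size, not a forecast for the H2 interaction. The documents support neither a charge that the SAP has settled on a cut nor one that it contradicts the protocol. H1 is not affected.

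**What to change.** In SAP 3.3.1, before the ratings are analysed:

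- Pre-specify a cumulative-logit mixed model on the two overall 4-point items (diagnosing, managing), with the same arm-by-time term, and report the common relative odds ratio with its 95% confidence interval.
- Keep the component items and any composites as further analyses, in line with Protocol 9.4.2.
- Fix the two-level cut used in the pilot tables (*moderately/very* against *a little/not at all*) as a supportive analysis. Make it the fallback if proportional odds clearly fails or an extreme level is too sparse, and write down how that will be judged.
- Replace the conditional sentence in SAP 2.4.2.1 so that it points to this rule.

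The cost is SAP wording and a different link option in the model; data collection does not change. The downside is a proportional-odds assumption that must be checked, possibly with few responses in the extreme levels.

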#### 2.4.2.2 Clinician survey administration

All eligible primary care clinicians practicing in all randomized study clinics will be invited to complete a pre-implementation PCC survey prior to clinician training on CI-CDS or its implementation in study clinics. Similarly, all primary care clinicians practicing in all randomized clinics approximately 8 months after CI-CDS implementation will be invited to complete a post-implementation PCC survey. The invitation to complete the post-implementation survey will not depend on having practiced at the clinic prior to CI-CDS implementation or upon completion of

the pre-implementation PCC survey. PCCs will be assigned to their primary clinic location and its randomized treatment group.

Invitations to complete each survey will be emailed to clinicians with a personalized link for completing the survey online. Reminder emails will be sent to clinicians who do not respond. An electronic gift card will be offered as a thank you for completing each survey.

Both surveys will include items to measure clinician confidence in diagnosing and managing care for CI as well as other barriers related to CI care and diagnosis. The post-implementation surveys emailed to clinicians who practice at CI-CDS clinics will include items regarding their use and satisfaction with the CI-CDS.

#### **2.4.3 H3 outcomes (secondary): Cost and utilization**

Indicators of any use (utilization) of emergency department (ED), inpatient or both facility types between 365 days prior to the index visit and during the observation period, inclusive, will be calculated from data extracted from insurance claims databases. Additionally, the combined costs of ED and inpatient care delivered will be extracted as paid amounts for facility and professional services on ED and inpatient days. The data elements needed to calculate this outcome will be extracted at the conclusion of the observation period from insurance claims databases among ITT patients who have HealthPartners insurance.

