## LIST OF ABBREVIATIONS

Abbreviation	Definition
accrual period	time period when patients accrue into the study that begins at the same calendar time when the CI-CDS system is implemented in all clinics at a site and ends at a pre-determined calendar time
CDS	clinical decision support
CI	cognitive impairment
CI-CDS	cognitive impairment clinical decision support system
CONSORT	Consolidated Standards of Reporting Trials
DSMB	Data Safety Monitoring Board
ED	emergency department
EHR	electronic health record
EPIC	common EHR software system used by HealthPartners and other health systems to manage patient health records
GLM	generalized linear model
H<n>	Hypothesis <number>
ICC	intraclass correlation
ICD-10	International Classification of Diseases, 10 th Revision
index visit	first visit during the accrual period at a randomized clinic at which a patient meets all intervention eligibility criteria
intervention period	time period when the CI-CDS interface is operative in intervention clinics that begins at the same time as the accrual period and ends at a set calendar time
ITT	intent to treat
LMM	linear mixed model
MC-PLUS	algorithm developed in the R61 phase to identify patients at high risk of CI diagnosis
MCI	mild cognitive impairment
Mini-Cog	brief screening tool designed to help healthcare providers identify individuals who may have cognitive impairment
MMSE	Mini-Mental State Examination
MMM	Mayo Mini Mental
MoCA	Montreal Cognitive Assessment
NIH	National Institutes of Health
observation period	time period when patient outcome data accumulate that begins at the patient index visit and ends at the end of the intervention period

Abbreviation	Definition
OR	odds ratio
PCC	primary care clinician
PI	principal investigator
ROR	relative odds ratio
RR	risk ratio
SAP	Statistical Analysis Plan
SLUMS	St. Louis University Mental Status
UC	usual care

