#### **2.4.4 Pre-index characteristics**

The index visit functions as a baseline to the extent that patients will be described / stratified according to characteristics that were documented at the beginning of the index visit, prior to potential intervention exposure. Patient information documented in the EHR or health plan claims databases on or prior to the index visit will be used to describe pre-intervention patient characteristics (e.g., age on index date, sex, risk of CI diagnosis at index visit), organize patients into groups to assess treatment heterogeneity (e.g., insurance status) or calculate pre-index values (e.g., healthcare utilization in pre-index year). All metrics needed for baseline characterization or reference are either already available in historical databases or will be documented in the course of care delivery. None will be assessed solely for research purposes.

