### 3.2 Primary effectiveness analysis

The H1 effectiveness analyses – comparing likelihood of CI recognition across treatment arms – will be carried out using the ITT sample data: patients accrued from CI-CDS and UC clinics who are at elevated risk for CI but without a CI diagnosis prior to their index visit and not on a research exclusion list. Descriptive statistics will be used to characterize, overall and by treatment arm, the proportion of ITT sample patients who have CI recognized during the observation period, the time elapsed between study accrual and recognition and the clinic intraclass correlation in CI recognition. H1 will be tested using a generalized linear mixed model (LMM) to account for clustering within randomized clinics and normalize the binary outcome via a distribution-appropriate link function (e.g., logit, log). The model will include fixed effects for clinic-randomized treatment group and any patient covariates (e.g., age, sex, predicted risk score) and a random clinic intercept:

$$\text{logit}(\text{diagnosis}_{ji}) = \gamma_{00} + \gamma_{10}\text{CI-CDS}_j + \gamma_{0*}(\text{pt covars})_{ji} + [v_j], \quad \text{where } j=\text{clinic, } i=\text{patient.}$$

Parameter  $\gamma_{10}$  is expected to be positive and statistically significant, indicating that patients in clinics randomly assigned to CI-CDS are more likely to receive a CI diagnosis in the observation period than patients in UC clinics. Model-estimated outcomes will be calculated by treatment group, and the treatment effect will be presented as an odds ratio (OR, or risk ratio [RR]) and its 95% confidence interval.

A secondary model will add a fixed coefficient that represents time elapsed between the index visit and the first EHR-documented CI diagnosis, or zero for those lacking a CI diagnosis, and the interaction between treatment group and time. The time covariate will be coded as (days since index)/365 so that it quantifies the predicted annual change in CI diagnosis rates. The time parameter is expected to be near zero and not statistically significant. Should the time elapsed between index and CI diagnosis differ by treatment group, log (observation time) may be included as an offset in the primary analysis.

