#### 3.3.2 Cost and utilization (H3).

The H3 cost analyses – comparing healthcare utilization costs related to emergency room and inpatient visits in the observation period by treatment arm – will be carried out using data from the subset of ITT patients who have HealthPartners insurance. Descriptive statistics will be used to compare the characteristics of patients by insurance status and treatment arm, and to summarize utilization (e.g., proportion of patients with a post-index inpatient stay) and cost (e.g., median cost of ED visits) outcomes overall and by treatment arm. Secondary H3 analyses may be conditioned on pre-index patient characteristics that differ by treatment arm.

H3 predicts that patients accrued from CI-CDS clinics will have lower post-index health care utilization costs related to emergency room and inpatient visits, relative to those accrued from UC clinics. Anticipating a zero-mass of patients with no emergency department or inpatient costs, we will employ a 2-part model to test H3. In the first part, the probability that patients will experience one or more emergency department visits or inpatient stays will be assessed using logistic regression in the same form as was used for H1. The second part will employ a generalized linear model (GLM) allowing clustering by clinic and controlling for demographics and baseline risk. Such analyses often specify a gamma distribution for health care expenditures with a log link function of the explanatory variables. We will choose the distribution family based upon the data using a modified Park test and choose the link function using a Box-Cox test. If we observe a statistically significant difference in emergency department and inpatient costs in the CI-CDS group, we will use similar methods to assess whether total costs of care, including all outpatient care and pharmacy, are also lower.

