### **4.2 Safety events**

Safety events will be monitored via passive surveillance of EHR and administrative data sources maintained by the health system, and state mortality data, for all safety population patients. Benefits to this approach are that safety events can be ascertained identically for all accrued patients in all randomized clinics. Documentation will occur while delivering health care or administering health insurance so that records should be reasonably accurate and complete with minimal and randomly missing information. When care for safety events is delivered outside the care system, health care claims can document their occurrence for patients who are also health plan members. Missing information due to events for which patients do not seek care or care that escapes documentation in the EHR or claims will be assumed to occur equally across treatment groups.

We will monitor emergency department (ED) visits, hospitalizations, suicide attempts, and deaths as safety events among all accrued patients from one year prior to their index visit through the end of the observation period. ED and hospital encounter dates, and suicide attempt and self-harm diagnosis code dates, will be used to determine whether safety events occurred pre- (365 to 1 days prior to index) or post-index (on the index visit date through the lesser of date of death or observation period end).

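### SAP 2.4.3 runs the H3 any-use outcome from 365 days before the index visit, in conflict with the protocol and with the post-index framing of H3 elsewhere in the SAP

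*SAP*

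**What the plan says.** SAP 2.4.3, headed as the H3 outcomes, sets the window for the any-use indicators (ED, inpatient or both): "inpatient or both facility types between 365 days prior to the index visit and during the observation period, inclusive". It does not divide that span into two periods. The next sentence, on ED and inpatient costs, gives no window.

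Protocol 9.4.2 describes the same indicators as "Indicators of any use of emergency room (ER), inpatient or both facility types between the index visit and of the observation period, inclusive". A word such as *end* is evidently missing, but the start is plainly the index visit.

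The SAP list of abbreviations defines the observation period as the "time period when patient outcome data accumulate that begins at the patient index visit and ends at the end of the intervention period". Protocol 9.5.3 states that "H3 predicts that patients accrued from CI-CDS clinics will have lower post-index health care utilization", and SAP 3.3.2 states the hypothesis as "lower post-index health care utilization costs related to emergency room and inpatient visits".

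Two other SAP sections use the same look-back as a baseline. SAP 2.4.4 says that pre-index information will be used, among other things, to "calculate pre-index values (e.g., healthcare utilization in pre-index year". SAP 4.2 classifies safety events by whether they "occurred pre- (365 to 1 days prior to index) or post-index (on the index visit date through the lesser of date of death" or the end of observation.

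**The concern.** An outcome window that opens a year before the index visit includes care that the intervention cannot have affected. A patient admitted once in the prior year, with no ED or inpatient use afterwards, would count as having the H3 outcome. Such patients occur in both arms. They add events unrelated to treatment and pull the arms together in part 1 of the two-part model, which compares the probability of any use.

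The SAP presents itself as expanding on the protocol's statistical section, so a programmer could take the longer window in SAP 2.4.3 as a deliberate refinement. It is also the only place in the SAP that attaches explicit dates to the any-use indicator.

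A smaller question follows. If the prior year is meant as a baseline, the plan does not say whether it enters the H3 model.

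**Working it through.** **1. The passages side by side**

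| Place | Period for H3 |
|---|---|
| Protocol 9.4.2 | from the index visit |
| Protocol 9.5.3 | post-index |
| SAP list of abbreviations | outcome data accumulate from the index visit |
| SAP 3.3.2 | cost comparison placed in the observation period; utilization summary illustrated by post-index inpatient stays; hypothesis worded as post-index |
| SAP 2.4.3, any use | from 365 days before index through the observation period |
| SAP 2.4.3, cost | no window stated |

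SAP 2.4.3 stands alone on any use. The conflict does not extend to its cost sentence.

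**2. Effect of the literal window**

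The plan states no use rate, sample size or power for H3, so there is no figure to reproduce. Write p for the proportion with pre-index use, taken as equal in the two arms. In each arm:

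rate in literal window = p + (1 − p) × P(post-index use | no pre-index use)

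The arm difference in the literal window is therefore (1 − p) × the difference in P(post-index use | no pre-index use). Under independence of the two periods, the true difference is multiplied by (1 − p).

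All inputs below are **assumed**: post-index any use 40% in usual care (UC) and 35% in CI-CDS (5.0 points; odds ratio (0.35/0.65)/(0.40/0.60) = 0.81); p = 25%, 35% or 45%; correlation r between the periods 0.2, 0.3 or 0.5. For UC, P(pre and post) = p × 0.40 + r × √(p(1 − p) × 0.40 × 0.60). For CI-CDS, one odds ratio common to pre-index users and non-users is solved so that overall post-index use is 35%.

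| p | UC vs CI-CDS, literal window (r = 0.2; 0.3; 0.5) | Difference, points | Odds ratio |
|---|---|---|---|
| 25% | 50.8 vs 47.1; 48.6 vs 45.0; 44.4 vs 40.5 | 3.62; 3.63; 3.86 | 0.865; 0.864; 0.854 |
| 35% | 56.3 vs 53.3; 54.0 vs 51.0; 49.3 vs 46.4 | 3.06; 2.99; 2.93 | 0.884; 0.887; 0.889 |
| 45% | 62.1 vs 59.6; 59.7 vs 57.3; 54.8 vs 52.7 | 2.51; 2.38; 2.07 | 0.900; 0.907; 0.920 |

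Differences come from unrounded rates. For p = 35% and r = 0.2, P(post-index use | no pre-index use) is 32.81% in UC and 28.11% in CI-CDS. The difference is 0.65 × (32.81 − 28.11) = 3.06 points.

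**3. Effect of the baseline reading**

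If SAP 2.4.3 means one indicator for the prior year and another for the observation period, only the second is the outcome and nothing is diluted.

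**4. Does baseline use enter the model?**

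Part 1 takes the H1 form, which has "any patient covariates (e.g., age, sex, predicted risk score" as examples. Part 2 adjusts for demographics and a baseline risk that is not defined. SAP 3.3.2 also allows, without requiring it, secondary H3 analyses conditioned on pre-index characteristics that differ by arm. Pre-index use is neither named nor ruled out.

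**The case against.** The strongest reply is that SAP 2.4.3 is only loosely worded. It speaks of indicators in the plural, and its phrasing fits a pre-index and a post-index indicator written as one. SAP 2.4.4 lists prior-year utilization as a baseline value, SAP 4.2 splits the same look-back explicitly, and SAP 3.3.2 places the H3 comparison after the index visit. This stands, and it makes the baseline reading the likelier one. It does not cure the text: the split written for safety events is missing from the section that defines the H3 outcomes, and the protocol gives a different start date.

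A second reply is that adjustment for prior use is a choice of efficiency that the documents never promised. This also stands. Clinics are randomized, so omitting the covariate is not a bias, and it contradicts nothing in the plan.

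A third is that a claims-based baseline may be incomplete. SAP 2.4.3 selects patients with HealthPartners insurance and states no requirement for coverage before the index visit. In addition, its look-back attaches to any use only, and SAP 2.4.4 names utilization and not cost. Pre-index cost therefore cannot be assumed to be part of the planned extract. The fix takes account of both.

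**Conclusion.** The contradiction in the any-use window is real and should be corrected. Its practical size is unknown. It is zero if the look-back is a baseline extract. If the literal window is used, a true 5.0-point difference would shrink to about 2.1 to 3.9 points, and the odds ratio would move from 0.81 to between 0.85 and 0.92. Those figures rest wholly on assumed rates, an assumed effect and assumed correlations, under the less likely reading.

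Three stronger conclusions might be inferred, and the documents support none of them:

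- That H3 will be tested on the longer window. SAP 3.3.2 itself points to the observation period.
- That the cost outcome includes the prior year. The cost sentence states no window.
- That leaving prior use out of the model biases H3. It costs precision only.

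H3 is a secondary hypothesis. The H1 outcome has its own definition, which starts at the index visit, and is unaffected.

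**What to change.** **SAP 2.4.3.** Define the H3 any-use and cost outcomes from the index visit date through the end of the observation period. Define any ED or inpatient use from 365 to 1 days before index as a separate baseline variable, with the same split as SAP 4.2.

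**SAP 3.3.2.** As an improvement in precision, pre-specify baseline any use as a fixed effect in both parts of the H3 model, with an indicator for patients who lack a full pre-index year of HealthPartners coverage. Add pre-index cost to part 2 only if the same claims extract supplies it.

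**Cost.** A few sentences in the SAP. Prior-year utilization is already planned, and the H3 data are to be extracted only when observation ends. The added work is to determine prior-year coverage for each insured patient and to handle those whose coverage is incomplete.
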